3.4. Per-Protocol Analysis Set

The per-protocol (PP) analysis set will consist of all patients who have completed the study without any violations of the inclusion/exclusion criteria or any violations or omissions of the drug administration.

In the PP analysis set, treatment will be assigned based on the treatment to which patients were randomized, regardless of which treatment they actually received.

The efficacy analysis for the primary and secondary endpoints will be repeated for the per-protocol analysis set.

3.5.

[REDACTED]

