9.2.4. Per-Protocol Analysis Set

The per-protocol (PP) analysis set is a subset of the ITT analysis set including only patients without any important protocol deviations. Important protocol deviations will be determined before unblinding/database lock.

In the PP analysis set, treatment will be assigned based on the treatment patients actually received, regardless of the treatment to which they were randomized.

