APPENDIX C. QUALITY CONTROL AND QUALITY ASSURANCE

Protocol Amendments and Protocol Deviations

Protocol Amendments

No changes from the final approved (signed) protocol will be initiated without the prior written approval or favorable opinion of a written amendment by the Independent Ethics Committee/Institutional Review Board (IEC/IRB) and national and local competent authorities, as applicable, except when necessary to address immediate safety concerns to the patients or when the change involves only nonsubstantial logistics or administration. The principal investigator at each investigational center, the coordinating investigator (if applicable), and the sponsor will sign the protocol amendment.

Protocol Deviations

Any deviation from the protocol that affects, to a significant degree, (a) the safety, physical, or mental integrity of the patients in the study and/or (b) the scientific value of the study will be considered an important protocol deviation. Important protocol deviations may include non-adherence on the part of the patient, the investigator, or the sponsor to protocol-specific inclusion and exclusion criteria, primary objective variable criteria, or GCP guidelines; noncompliance to IMP administration; use of prohibited medications. All protocol deviations will be reported to the responsible IEC/IRB, as required.

When an important protocol deviation is reported, the sponsor will determine whether to discontinue the patient from the study or permit the patient to continue in the study, with documented approval from the medical expert. The decision will be based on ensuring the safety of the patient and preserving the integrity of the study. A noncompliant patient may continue taking the study treatment only if this does not jeopardize the patient's safety. The sponsor will assess each protocol deviation and decide whether any of these noncompliances should be reported to the Regulatory Authority as a serious breach of GCP and the protocol.

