15. STATISTICAL SOFTWARE

All data listings, summaries, and statistical analyses will be generated using SAS[®].

**16. CHANGES TO ANALYSES SPECIFIED IN THE STUDY
PROTOCOL**

None.

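### The SAP's per-protocol set requires completing the 12-week study even for the week 0 to 4 endpoints, and departs from the protocol's definition without saying so

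*SAP*

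**What the plan says.** SAP 3.4 admits to the PP set "all patients who have completed the study without any violations of the inclusion/exclusion criteria or any violations or omissions of the drug administration". It adds: "The efficacy analysis for the primary and secondary endpoints will be repeated for the per-protocol analysis set". SAP 6.1 and 6.3 confirm that this one set serves the primary and all secondary endpoints. On treatment assignment SAP 3.4 says: "In the PP analysis set, treatment will be assigned based on the treatment to which patients were randomized, regardless of which treatment they actually received".

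Protocol 9.2.4 describes a different set. It "is a subset of the ITT analysis set including only patients without any important protocol deviations", with the deviations to be settled before unblinding. It has no completion rule, and assignment goes the other way: "In the PP analysis set, treatment will be assigned based on the treatment patients actually received, regardless of the treatment to which they were randomized". Protocol Appendix C counts a deviation as important when it affects patient safety or scientific value to a significant degree. Its possible examples include eligibility, primary objective variable criteria, GCP, and "noncompliance to IMP administration; use of prohibited medications".

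The timing matters here. The primary endpoint and the first secondary endpoint (50% responders) use week 0 to 4 data (SAP 1.1 and 1.2). The final visit is at about week 12 (SAP 2.1). The second and third doses are given at weeks 4 and 8.

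Three further texts bear on the point:
- SAP Section 16, under the heading that begins "CHANGES TO ANALYSES SPECIFIED IN THE STUDY", has the one-word entry None.
- The SAP Introduction says that the SAP takes precedence over the protocol and that differences will be explained in the study report.
- SAP 6.1.4.1 also removes patients with fewer than 10 e-diary days in the first 4 weeks from the PP set. SAP 3.4 does not state this rule.

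**The concern.** For the two week 0 to 4 endpoints, PP membership depends on what happens after the outcome has been observed. Two patients with identical first doses and identical four-week diaries are treated differently if one withdraws at week 9.

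That later event need not be neutral. Protocol 3.4 and 4.3 both name lack of efficacy as a reason for withdrawal, so a poor four-week result can itself lead to the patient's removal from the four-week PP analysis. In the 675-mg sc and placebo arms the week 4 and week 8 injections are placebo. Omitting one changes no active exposure, yet it still removes the patient.

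A PP analysis is read next to the full analysis set (FAS) to see whether departures from the protocol matter. If the two disagree here, part of the difference may come from selection on later retention, and the reader could not separate the two sources. Section 16 also gives a reader of the SAP no signal that the set differs from the one in the protocol.

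**Working it through.** **1. The plan's own figure.** Inputs from Protocol 9.1: difference 1, SD 2, two-sided alpha 0.05, power 90%, 86 completers per group, 14% discontinuation.
- n per group = 2 × (1.960 + 1.282)² × 2² / 1² = 84.1, rounded up to 85. The plan states 86.
- Power with 86 per group is 90.6% (90.3% by the noncentral t).
- 3 × 86 = 258, and 258 / 0.86 = 300. The plan's figures reproduce.

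**2. How many fail the SAP rule on completion alone.** 300 × 0.14 = 42, so the PP set is at most about 258.

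**3. How many of the 42 leave after week 4.** The documents give no timing, so the share is an assumption:
- 25% late: 42 × 0.25 = 10.5
- spread evenly over 12 weeks: 42 × 8/12 = 28
- constant hazard: 300 × (0.86^(1/3) − 0.86) = 27.3
- 75% late: 42 × 0.75 = 31.5

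The range is about 10 to 32 of 300, with a ceiling of 42. Omitted week 4 or week 8 doses in patients who complete would add to it; the documents give no rate for these.

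**4. What it could do to the estimate.** If w of n patients in an arm are removed and they average d attacks per week worse than those kept, the arm mean improves by w × d / n. As an illustration, assume 95 patients per arm reach week 4, d = 2 (one planning SD), and late withdrawals of 14 on placebo and 7 in each active arm (28 in all).
- Placebo: 14 × 2 / 95 = 0.295
- Each active arm: 7 × 2 / 95 = 0.147
- Each active-versus-placebo contrast shrinks by 0.295 − 0.147 = 0.15, or 15% of the planned difference of 1.

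If w and d are equal across arms, the shifts cancel.

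**5. The two definitions side by side.**

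| | Protocol 9.2.4 | SAP 3.4 |
|---|---|---|
| Completion | not required | required |
| Exclusions | important deviations | any eligibility violation; any dosing violation or omission |
| Prohibited medication | possible important deviation (Appendix C) | not listed |
| Treatment | as received | as randomized |

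The sets differ in both directions. The SAP adds completion and drops the test of importance, but it does not list prohibited medication. Protocol 4.3 requires withdrawal for prohibited medication, while Appendix C lets the sponsor permit continuation after an important deviation. Such a patient who completes could stay in the SAP set.

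**6. The responder endpoint.** Protocol 9.3.1 counts early terminations as non-responders. On that text a patient who leaves at week 9 is a non-responder in the FAS and absent from PP, so the two can differ mechanically. The SAP's own rule (6.1.4.2) is redacted, so this cannot be confirmed.

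**The case against.** The strongest reply is that nothing decisive depends on this set. SAP 6.1 makes the FAS the set for efficacy, later withdrawal or missed later doses remove nobody from it, and no visible text attaches a decision to the PP result. A single completer-type PP set in a supporting role is a common convention. All of this stands, and it caps the importance of the point. A reader might infer that the primary result is compromised; the documents do not support that.

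Other stronger readings also fail or need limits:
- **Treatment assignment.** A reader might infer that the reversed rules would give materially different results. A patient given the wrong treatment would normally count as a dosing violation and leave the SAP set, so the two rules should nearly always coincide there. The texts still need reconciling.
- **Missed later doses.** A reader might infer that only the SAP excludes for these. The protocol set has no day-28 cut-off and its important deviations may include dosing noncompliance, so a missed week 8 dose could exclude under either text. Only the completion rule is clearly new.
- **Adherence.** A reader might infer that any PP–FAS difference would have nothing to do with adherence. Omitting a scheduled dose is non-adherence, and so is withdrawal for noncompliance or prohibited medication (Protocol 4.3). The objection is to using these events to select for an outcome already observed.
- **Precision.** With even dropout, losing 28 of 300 raises the standard error by a factor of 1/√(1 − 0.093) = 1.05. That compares with keeping late leavers, not with the plan, which sized the trial on 258 completers.

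The precedence clause settles which text governs. It neither makes Section 16's entry correct nor removes the selection. The undeclared change is not peculiar to PP: the FAS definition also moved between Protocol 9.2.3 and SAP 3.3. SAP 3.5 and text beside the PP references in SAP 6.1 and 6.3 are redacted, so another supporting set may exist. SAP 3.4 itself is fully visible.

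**Conclusion.** The point holds, as a minor one. For the primary and 50% responder endpoints, SAP 3.4 conditions PP membership on retention and dosing after the outcome window, and it differs from Protocol 9.2.4 while SAP Section 16 declares no change. These facts come from current text and need no assumption.

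The size does rest on assumptions. About 10 to 32 of 300 patients would be excluded for late withdrawal if 25% to 75% of the planned 14% discontinuation falls after week 4. Bias in the PP estimate arises only if late withdrawal is related to outcome and differs by arm. The 0.15-attack shift illustrates one such pattern and is not a forecast. The damage is confined to how the supportive PP analysis can be read; the error rate and power of the FAS primary test do not change.

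**What to change.** Before unblinding, amend the SAP as follows:
- For endpoints based on weeks 0 to 4, define the PP set by eligibility, correct first-dose administration, and no important deviation up to day 28. Keep the 10-diary-day rule of SAP 6.1.4.1 and state it in SAP 3.4.
- Apply the completion and later-dose rules only to endpoints that use later data.
- State one treatment-assignment rule for the PP set and reconcile it with Protocol 9.2.4.
- List the departure from Protocol 9.2.4 in SAP Section 16.

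The cost is SAP wording, one extra flag in the analysis dataset, and two PP sets to define and report instead of one. No data collection or trial conduct changes.

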4. GENERAL ISSUES FOR DATA ANALYSIS

4.1. General

Descriptive statistics for continuous variables include count (n), mean, SD, standard error (SE), median, minimum, and maximum. In addition, for fremanezumab concentration percentage coefficient of variation (%CV) and geometric mean will also be calculated. Descriptive statistics for categorical variables include patient counts and percentages, and a missing category will be displayed as appropriate.

Summaries of potentially clinically significant abnormal values for clinical laboratory tests and vital signs values will include all postbaseline values (including scheduled, unscheduled, and early withdrawal visits).

4.2. Specification of Baseline Values

Baseline is the last observed data before the administration of the first dose of the IMP, unless otherwise noted. For data collected in the e-diary daily, baseline will be derived from the run-in period (including days from the informed consent up to the day prior to the first dose of the IMP administration) and prorated to 7 days if the number of days in the run-in period is not equal to 7. Details are provided in Section 6.1.

4.3. Region of Pooled Countries

The study is planned to be conducted in approximately 12 countries. The countries will be pooled to 2 regions (US/Canada and other).

4.4. Handling Withdrawals and Missing Data

For efficacy analyses using e-diary data, the missing data handling methods are provided in Section 6.1.4. For the efficacy analyses using non-e-diary data, missing data handling methods, if applicable, will be provided in the efficacy analysis section for that endpoint.

4.5. Study Days and Visits

For by-visit summaries, if there are multiple assessments at a postbaseline visit then the last non-missing assessment at that visit will be used for the summary (this includes scheduled and

unscheduled assessments), except for triplicate ECG assessments (see Section 8.11 for further details).

Study visits are detailed in Table 1.

Table 1: Study Visits

Visit #	V1	V2	V3	V4	V5
Week #	Week -1	Week 0	Week 4	Week 8	Week 12
Visit	Screening	Baseline	Visit 3	Visit 4	EOT/early withdrawal (84 ±3 days)

Notes: EOT=end of treatment; V2/Week 0 is day 1, which is the day eligible patients are randomized and receive first dose of IMP.

‘Last Assessment’ may be derived for analysis purpose and is defined as the last observed postbaseline data. For patients who withdraw from the study, their data at the early withdrawal visit will be excluded from the by-visit sections but will be included in the Last Assessment section.

Study days are numbered relative to the first day of the IMP administration. The start of treatment (day 1) is defined as the date on which a patient takes the first dose of the IMP, as recorded on the case report form (CRF). Days will be numbered relative to treatment start (ie, ..., -2, -1, 1, 2, ...; with day 1 being the first day of the IMP administration and day -1 being the day before the first day of the IMP administration).

For data from the e-diary, weekly analysis windows (week 1, week 2, etc.) and 4-week analysis windows (weeks 1 to 4, weeks 5 to 8, and weeks 9 to 12) will be derived for the purpose of efficacy endpoint analyses. Details are provided in Section 6.1.3.

5. STUDY POPULATION

5.1. General

The ITT analysis set (see Section 3.1) will be used for all study population summaries unless otherwise specified. Summaries will be presented by treatment group and for all patients.

5.2. Patient Disposition

Data from patients screened; patients screened but not randomized and reason for not randomized; patients who are randomized; patients randomized but not treated; patients in the ITT, safety, and other analysis sets; patients who complete the study; patients who withdraw from the study; and patients continuing into the long-term safety study will be summarized using descriptive statistics. Data from patients who withdraw from the study will also be summarized by reason for withdrawal using descriptive statistics.

Patients who consent to the wearable sensor substudy and their completion status (completed and reason for not-completed the substudy) will be summarized using descriptive statistics.

This summary will include all patients.

5.3. Demographics and Baseline Characteristics

The demographic data will be collected at the screening visit after the patient signs the informed consent form. Patient's demographics data including age, age group (<40 years or ≥40 years), gender, race, race group (white or other), ethnicity, region (US/Canada or other), baseline weight (kg), baseline height (cm), and baseline body mass index (kg/m²) will be summarized using descriptive statistics for all analysis sets.

Baseline characteristics including years since first ECH diagnosis, preventive medication use (yes or no) at screening or baseline, use of any triptans/ergots during the run-in period (yes or no), and number of CH attacks during the run-in period will be summarized for the ITT analysis set [REDACTED] using descriptive statistics. No inferential analyses will be performed.

5.4. Medical History

All medical history abnormalities will be coded using the Medical Dictionary for Regulatory Activities (MedDRA). The incidence of medical history abnormalities will be summarized using descriptive statistics by system organ class (SOC) and preferred term. Patients are counted only once in each SOC and only once in each preferred term.

5.5. Prior Therapy and Medication

All prior medications or therapy will be coded using the World Health Organization Drug Dictionary of medical codes (WHO Drug). The incidence of prior medications or therapy will be

summarized by therapeutic class and preferred term using descriptive statistics. Patients are counted only once in each therapeutic class category, and only once in each preferred term category. Prior medications will include all medications taken prior to the administration of the first dose of the IMP.

The prior medications will be summarized by the following indications categories:

- preventive medication from Appendix H of the study protocol for CH
- preventive medication from Appendix H of the study protocol for other reason than CH
- butalbital for CH
- butalbital for other reason than CH
- triptans for CH
- triptans for other reason than CH
- ergots for CH
- ergots for other reason than CH
- non-steroidal anti-inflammatory drugs (NSAIDs) for CH
- NSAIDs for other reason than CH
- opioids for CH
- opioids for other reason than CH
- other

5.6. Childbearing Potential and Methods of Contraception

Information related to reproductive system findings will be collected at the screening visit. Data will be listed.

5.7. Physical Examinations

Patients with at least 1 abnormal finding (overall) and abnormal findings for each category will be summarized.

5.8. Study Protocol Deviations

Data from patients with any important protocol deviations during the study will be summarized overall and for each category using descriptive statistics.

6. EFFICACY ANALYSIS

6.1. General

The FAS will be used for all efficacy analyses unless otherwise noted. Analyses of the primary and secondary endpoints will be repeated for the PP analysis set [REDACTED].

For data not collected daily, baseline is the last observed data before the administration of the first dose of the IMP. For data collected daily in the e-diary, baseline will be derived from the run-in period (including days from the informed consent up to the day prior to the first dose of the IMP administration). Details are provided in Section 6.1.3. The efficacy baseline value derived from the run-in period are

- number of CH attacks
- number of CH attacks of at least severe severity
- number of days with use of cluster-specific acute headache medication (triptans and ergot compounds)
- number of days with use of any acute headache medication
- number of days oxygen is used
- severity of CH attacks

Summaries will be presented by treatment group as randomized unless otherwise noted. In addition to inferential statistics, descriptive statistics will be presented by-visit or by-analysis-window summaries.

6.1.1. Cluster Headache Attacks Data from E-diary

[REDACTED]

6.1.2. Data Derivation

The *weekly average/value* of an efficacy endpoint will be calculated and prorated to 7 days as follow:

$$\frac{\sum \text{efficacy endpoint data during the period}}{\text{Number of Days with assessments recorded in the eDiary during the period}} \times 7 \quad [1]$$

The “efficacy endpoint data” will be “number of CH attacks”, “days with use of cluster-specific acute headache medications (triptans and ergot compounds)”, “days oxygen is used to treat ECH”, or “days with use of any headache medication”, etc.

The period will be the run-in period (including days from the informed consent up to the day prior to the first dose of the IMP administration) for baseline calculation or an analysis window (eg. weeks 1 to 4, weeks 5 to 8, weeks 9 to 12, etc.) for post-baseline calculations.

[REDACTED]

6.1.3. Analysis Windows for E-diary Data

Baseline window is the run-in period and includes days from the informed consent to the day prior to the first dose of the IMP administration. The baseline weekly average value for an efficacy variable will be calculated based on data recorded in the run-in period and prorated to 7 days using formula [1].

Note, per eligibility checks at visit 2, patients with more than 10 days in the run-in period will not be eligible and will not be randomized for the study. However, in case there are patients with more than 10 days of the e-diary data collected during the run-in period, all data will be used for the baseline calculation by prorating the data to 7 days.

[REDACTED]

6.1.4. Handling Missing E-diary Data

This section includes missing data handling for e-diary data. For other type of data, the missing data handling methods are provided in the analysis section for the endpoint if applicable.

6.1.4.1. Primary Efficacy Endpoint

The weekly average number of CH attacks during the 4-week period will be calculated based on data available and prorated to 7 days using formula [1]. Note, patients who have < 10 days of e-diary data in the first 4-week will be excluded from FAS and PP analysis set (Section 3).

As sensitivity analyses, the primary endpoint will be analyzed using the following methods for handling missing data :

- Multiple imputation (MI) method to impute missing weekly data
- An mixed model for repeated measures (MMRM) method to analyze the weekly data

Detail is provided in Section 6.2.3.

6.1.4.2. Analyses Based on Monthly and 12-week Window

[REDACTED]

[REDACTED]

- [REDACTED]
- [REDACTED]

[REDACTED]

- [REDACTED]
- [REDACTED]

[REDACTED]

6.2. Primary Efficacy Endpoint and Analysis

6.2.1. Definition

The primary efficacy endpoint of this study is the mean change from baseline (run-in period) in the weekly average number of CH attacks during the 4-week period after administration of the first dose of the IMP.

CH attacks will be derived from the e-diary data as described in Section 6.1.1. The analysis will be based on the weeks 1 to 4 analysis window, which will be derived using the algorithm described in Section 6.1.3. Missing data handling methods are provided in Section 6.1.4.1.

6.2.2. Primary Efficacy Analysis

The hypothesis testing for the primary analysis is:

$$H_o : \delta_1 = \delta_2 \quad \text{vs} \quad H_a : \delta_1 \neq \delta_2$$

where δ_1 and δ_2 are the estimates of mean change from baseline in the weekly average number of CH attacks for the fremanezumab treatment group and the placebo group, respectively. To

[REDACTED]

[REDACTED]

[REDACTED]

X_1 X_2 X_k

[REDACTED]

[REDACTED]

[REDACTED]

[REDACTED]

[REDACTED]

[REDACTED]

The analysis will be performed on the ITT analysis set.

